5. RANDOMISATION AND ENROLMENT PROCEDURE

5.1 RANDOMISATION OR REGISTRATION PRACTICALITIES

All the participants from each round will receive all the treatments/procedures in a randomised sequence order (using a cross-over design) that will be pre-organized by the researchers.

5.2 UNBLINDING (IF APPLICABLE)

All the participants will know which type of treatment they will be receiving throughout the testing process.

6. TRIAL TREATMENT

6.1 Name and description of investigational treatment product(s)

Supertowel:

The Supertowel is a durable fabric with a permanent anti-microbial treatment. The treated fabric must be dipped in water and then rubbed against the hands so that pathogens will be transferred to the fabric where they will be killed.

Soap:

Non-antimicrobial bar soap will be used as a reference product for three of the experiments.

6.2 Treatment of participants.

6.2.1. Contamination procedure:

The hands of each volunteer will be washed with a non-medicated soap, dried and fingers (up to the proximal interphalangeal joints) will be immersed for 5 seconds in a contamination fluid which contained non-pathogenic *Escherichia coli* (ATCC 11229) 8.3×10^8 cfu/ml. Excess of fluid will be drained off and hands will be air-dried for 3 min.

Pre value. Bacteria will be recovered for the initial pre value by kneading the fingertips of each hand separately for 60 seconds in 10 ml of tryptone soya broth (TSB) without neutralizers. The pre values will be estimated using the Miles *et al.* technique [16].

6.2.2. Hygienic hand-washing procedures/treatments:

Each volunteer will receive the following procedures/treatment in a pre-established random order over the course of one day.

Procedure 1.

- Treatment: Hand cleaning with the Supertowel for 15 seconds.

The Supertowel will be soaked in water by submersing it completely in a bucket filled with tap water. The amount of water absorbed by the ST will be recorded by means of weighing the towel before and after soaking. The volunteers will use the soaked Supertowel for 15 seconds to clean their pre-contaminated hands.

- Control: Hand washing with bar soap and water for 15 seconds.

The control group will wash their pre-contaminated hands with normal bar soap and water for 15 seconds. Hands from volunteers washed with soap will be allowed to dry for 3 minutes.

Prior to doing either of the conditions above, a laboratory technician will demonstrate to the volunteer how to use either the Supertowel or the bar soap for the required time. 15 sec, e.g. wetting hands for 5 seconds, lathering soap for 5 seconds and rinsing hands for 5 seconds).

Procedure 2.

- Treatment: Hand cleaning with a Supertowel that is damp for 60 seconds

The Supertowel will be soaked in water by submersing it completely in a bucket filled with tap water. The water on the Supertowel will then be squeezed out so that it is not dripping. The Supertowel will be weighed before soaking and after squeezing. Volunteers will clean their pre-contaminated hands with the damp Supertowel for 60 seconds.

- Control: Handwashing with bar soap and water for 60 seconds

The control group will wash their pre-contaminated hands with normal bar soap and water for 60 seconds by following the “WHO guidelines for handwashing when hands are visibly soiled” (a diagram of the steps was given to them, appendix). After handwashing, hands will be allowed to dry for 3 minutes.

Procedure 3.

- Treatment: Hand cleaning for 60 seconds with a Supertowel that has been soaked in contaminated water.

A Supertowel will be soaked in water which has artificially contaminated with non-pathogenic E.coli. The water will be designed to mimic highly contaminated grey water so it will be contaminated at 2,000 cfu/100 ml which is double the acceptable level of contamination for handwashing. Volunteers will clean their pre-contaminated hands with the contaminated Supertowel for 60 seconds.

Control: Handwashing with bar soap and water for 60 seconds.

Water which is contaminated with non-pathogenic E.coli. at 2,000 cfu/100ml will be stored in a bucket which has a tap at the base. The control group volunteers will wash their hands with the contaminated water and bar soap for 60 seconds. They will follow the “WHO guidelines for handwashing when hands are visibly soiled” (a diagram of the steps will be given to them). After handwashing, hands will be allowed to dry for 3 minutes.

Procedure 4.

- Treatment: Hand cleaning for 60 seconds with a Supertowel that is visibly dirty and oily.

The Supertowel will be made visibly dirty and oily for example, by immersing it in a mix of 5 grams of sterile soil (previously autoclaved), 5 ml of clean cooking oil and 100 ml of water (we will play in advance, to find out the most appropriate amounts of these products). The Supertowel will be rubbed against itself to ensure the soil and oil are spread out across the surface of the Supertowel. Volunteers will clean their pre-contaminated hands with the dirty Supertowel for 60 seconds.

- Control: Hand cleaning for 60 seconds with a clean Supertowel.

The Supertowel will be soaked in water by submersing it completely in a bucket filled with tap water. The amount of water absorbed by the ST will be recorded by means of weighing the Supertowel before and after soaking. The control group will clean their pre-contaminated hands of with the soaked Supertowel for 60 seconds.

Procedure 5.

Testing the Supertowel under a mix of aforementioned conditions. The exact design of this study will be determined after results of procedures 1-4 are obtained. For example, a possible test might be to assess whether a damp Supertowel is still efficacious when used for 15 seconds (combining procedure 1 and 2).

6.2.3.Post values. After drying of the hands, the thumbs and fingers of both left and right hands will be rubbed in separate petri dishes containing 10 ml of TSB for 60 seconds. Post values will be determined using the method of Miles *et al.* [16]. After the procedure, the volunteers will be given medicated soap to wash their hands before going home.

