9. STATISTICS AND DATA ANALYSIS

For all the procedures, log counts from the left and right hands of each subject will be averaged separately, for both pre and post values. The arithmetic means of all individual \log_{10} reduction values will be calculated. Statistical analysis will be performed with the Statistical Package STATA version 13.0. Wilcoxon matched-pair signed ranks test will be used to test for differences between each *Supertowel procedure* and their reference condition. The new procedure (*Supertowel under different conditions*) will be considered as effective as the reference product (soap) if the mean \log_{10} reduction factor is not significantly smaller for the former than for the latter. Because of the confirmative nature of the test on this application, the level of significance is set at $p = 0.1$. The test is to be used one-sided. The

discrimination efficiency of the test procedure described has been set to detect a difference between the two mean log reduction factors of approximately 0.6 log at a power of 95%. Data and all appropriate documentation will be stored for a minimum of 5 years after the completion of the study.

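### Pre values come from kneaded fingertips and post values from rubbed thumbs and fingers, so the absolute log10 reductions may carry an unknown offset; the paired test against the reference is not biased by it

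*Combined protocol and SAP*

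**What the plan says.** All references are to the combined protocol and SAP.

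- **Contamination (Section 6.2.1).** The "fingers (up to the proximal interphalangeal joints) will be immersed for 5 seconds" in the *E. coli* fluid. Thumbs are not named separately.
- **Pre value (Section 6.2.1).** Bacteria are recovered by "kneading the fingertips of each hand separately for 60 seconds" in "10 ml of tryptone soya broth (TSB) without neutralizers".
- **Post value (Section 6.2.3).** After the treatment, "the thumbs and fingers of both left and right hands will be rubbed in separate petri dishes", each dish "containing 10 ml of TSB for 60 seconds".
- **Counting.** The method is the same at both times: "The pre values will be estimated using the Miles" technique, and "Post values will be determined using the method of Miles".
- **Outcome and analysis.** The Study Summary and Section 3.1 define the outcome as the reduction in bacteria on pre-contaminated hands. Section 9 averages the log counts over the two hands, separately for pre and post, and then takes "The arithmetic means of all individual" log10 reductions. It compares each Supertowel procedure with its reference by a one-sided Wilcoxon matched-pairs test.

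**The concern.** A log10 reduction can be read as what the product removed only if the two counts behind it come from the same skin, recovered in the same way. Followed literally, the plan samples a smaller, kneaded site before treatment and a differently described, rubbed site afterwards. Part of every reported reduction would then reflect the change of site and technique rather than the product.

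What is at stake is the absolute figures. Section 2 asks whether a soiled and oily Supertowel is efficacious, and the control for that condition (Procedure 4 in Section 6.2.2) is a clean Supertowel, not soap. A reader judging that condition will look at the size of the reduction itself. The same applies to anyone who sets this study's mean reductions beside those from other work.

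**Working it through.** **Step 1. Compare the two samplings as written.**

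| Feature | Pre (6.2.1) | Post (6.2.3) | Same? |
|---|---|---|---|
| Site | fingertips | thumbs and fingers, extent not given | no |
| Motion | kneading | rubbing | no |
| Time | 60 s | 60 s | yes |
| Broth volume | 10 ml TSB | 10 ml TSB | yes |
| Neutralizers | stated to be absent | not mentioned | unclear |
| Hands | separate | separate | yes |
| Counting | technique of reference 16 | technique of reference 16 | yes |

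The two descriptions differ in site and motion.

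**Step 2. Isolate the mismatch.** Let F be the pre site and technique, and A the post site and technique, all counts on the log10 scale. For any condition,

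measured reduction = pre(F) − post(A) = [pre(A) − post(A)] + [pre(F) − pre(A)].

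The first bracket is the reduction on a single basis, A. The second is the whole of the mismatch. It contains only counts before treatment and how well each technique recovers them.

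**Step 3. Size of the offset.** If A covers k times the contaminated area of F, with equal recovery per unit area, then pre(F) − pre(A) = −log10(k). Every reduction is understated by log10(k).

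| Assumed k | Understatement, log10(k) |
|---|---|
| 1.25 | 0.10 |
| 1.5 | 0.18 |
| 2 | 0.30 |
| 3 | 0.48 |

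The documents give no value of k. The value 1.25 corresponds to five digits against four (5/4), which supposes that the pre sample omits the thumb and that thumbs are contaminated; neither is stated. Immersion stops at the proximal interphalangeal joints, so sampling beyond them adds no directly contaminated skin. If kneading and rubbing recover bacteria to different degrees, the offset could be larger, smaller or of opposite sign.

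**Step 4. Effect on the paired test.** Write the mismatch bracket as δ. The paired contrast is

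(reduction, reference) − (reduction, Supertowel) = (difference on basis A) + (δ reference − δ Supertowel).

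Contamination and pre sampling are described once, for all conditions, and come before any product is used. δ therefore has the same expectation in both conditions, and the last term has expectation zero.

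An illustration with 16 simulated pairs, the same offset log10(k) being added to every post count:

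| k | Mean reduction, reference | Mean reduction, test | Difference | One-sided p |
|---|---|---|---|---|
| 1 | 3.29 | 2.77 | 0.52 | 0.0008 |
| 2 | 2.99 | 2.47 | 0.52 | 0.0008 |
| 4 | 2.69 | 2.17 | 0.52 | 0.0008 |

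The absolute means move by log10(k); the difference and the p-value do not move.

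**Step 5. The plan's own figure.** Section 9 is set to detect about 0.6 log with 95% power. That is a difference between two mean reductions, from which log10(k) drops out, so the offsets in Step 3 should not be measured against it. This point does not challenge the power statement.

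**The case against.** The strongest reply is that the difference may be only loose wording. Time, volume, broth type, separation of hands and counting method all agree. The method is adapted from EN 1499, and Section 10.2 has staff trained on SOPs; neither the standard nor the SOPs can be seen here. This stands as a limit: the documents do not show that practice will differ. It does not remove the point, because a technician following the text would sample two different sites.

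A second reply is that the decision rule is comparative and a common offset cancels. This stands in full for the Wilcoxon test.

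A reader might infer a stronger claim: that cloth wiping and lathering clean fingertips, finger shafts and thumbs unequally, so part of the mismatch survives in the Supertowel-versus-soap contrast. The documents do not support this. By Step 2 the mismatch term contains no post-treatment count, so it cannot depend on how a product cleans. If one product misses the thumbs, or carries bacteria onto them, its post count rises; that is a real difference in performance on the sampled skin, not measurement error. A product-dependent error would arise only if the target were the fingertips alone, and Section 3.1 speaks of hands. For Procedure 4, where both conditions use a towel, the wiping-versus-lathering argument does not apply at all.

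Nor does the text say that whole fingers are sampled after treatment. Section 6.2.3 gives no extent, and its silence on neutralizers is not evidence that the two broths differ.

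**Conclusion.** The point holds for the absolute reductions. As written, pre and post counts are not on the same basis, and the mean log10 reduction of every condition may be offset by an unknown amount. On the assumption of equal recovery per unit area, the understatement is 0.10 log at k = 1.25 and 0.30 log at k = 2; k itself is assumed.

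The tests of each Supertowel procedure against its reference are not biased, provided that contamination and sampling are carried out alike in all conditions, as the plan describes. Run-to-run variation in the mismatch could add scatter to the paired differences, but not a systematic shift. The mismatch is therefore no reason to doubt the direction of a Supertowel-versus-soap result. It is a reason not to take the reported reductions at face value, above all for the soiled-towel question. The correction is specific and nearly free, so it should be made.

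**What to change.** Write one sampling instruction and use it in both Section 6.2.1 and Section 6.2.3: the same digits, the same area limited to the skin immersed in the contamination fluid, the same motion, 60 seconds, and 10 ml TSB, with the broth's neutralizer status stated at both times. State in Section 6.2.1 whether thumbs are immersed.

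If the two samplings are meant to differ, say so, give the reason, and note beside the mean reductions that they are not on a common basis.

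The cost is protocol and SOP wording only. Sample size, schedule and analysis are unchanged.

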2. STUDY OBJECTIVES

Test the efficacy of the Supertowel as a hand-cleaning product using simulations of ‘real-world’ hand cleaning conditions. This will be achieved by using an in vivo design with healthy volunteers in India and a protocol adapted from the European Committee for Standardization protocol (EN 1499) [15].

Tests will be designed to explore the following objectives:

- Is the Supertowel as efficacious as soap if used for hand-cleaning for a short period of time (ie. 15 seconds)?
- Is the Supertowel as efficacious as soap if used for hand-cleaning when moist rather than soaking wet?
- Is the Supertowel efficacious for hand-cleaning if soiled and oily?
- Is a Supertowel soaked in contaminated water and then used for hand cleaning more efficacious than handwashing with soap and contaminated water?

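### Procedure 4 wets the dirty towel and its clean control by different steps and states a weighing only for the control, so the effect of dirt may be mixed with an effect of wetness

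*Combined protocol and SAP*

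**What the plan says.** Procedure 4 (section 6.2.2) compares a visibly dirty, oily Supertowel with a clean one, each used for 60 seconds.

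- **Dirty towel.** It is immersed in, for example, a "mix of 5 grams of sterile soil (previously autoclaved), 5 ml of clean cooking oil and 100 ml of water". The amounts are provisional: "we will play in advance, to find out the most appropriate amounts of these products". Then "The Supertowel will be rubbed against itself to ensure the soil and oil are spread out across the surface of the Supertowel". No later soak and no weighing are stated.
- **Clean control.** Its wetting is described as follows: "The Supertowel will be soaked in water by submersing it completely in a bucket filled with tap water". For this towel, unlike the dirty one, a measurement of uptake is stated: "The amount of water absorbed by the ST will be recorded by means of weighing the Supertowel before and after soaking".

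Section 2 keeps two questions apart. Objective 2 is about wetness: "Is the Supertowel as efficacious as soap if used for hand-cleaning when moist rather than soaking wet"? Objective 3, which Procedure 4 serves, is about dirt: "Is the Supertowel efficacious for hand-cleaning if soiled and oily"? For the damp towel of Procedure 2, water is also tracked: "The Supertowel will be weighed before soaking and after squeezing".

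Section 9 compares each towel procedure with its reference by a one-sided Wilcoxon matched-pairs test at 0.1. It includes no adjustment for water content.

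**The concern.** Procedure 4 is the only round 1 comparison of towel with towel, so its value lies in changing one thing: the dirt. As written, it changes the wetting method too, and it does so for every volunteer. The crossover removes differences between people but not a difference built into how the two towels are prepared.

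If the dirty towel does worse, the comparison cannot cleanly separate soil and oil from a difference in water content. If it does no worse, a wetness difference may have offset a real loss from dirt. Round 2 is exposed as well, because Procedure 5 is to be designed from the results of Procedures 1 to 4.

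**Working it through.** **1. The two preparations side by side (section 6.2.2, Procedure 4)**

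| Step | Dirty towel | Clean control |
|---|---|---|
| Water source | Small mix, example 100 ml water | Bucket of tap water |
| Wetting | Immersion in the mix | Full submersion |
| Afterwards | Rubbed against itself | No rubbing stated |
| Weighing | None stated | Before and after |

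Nothing in sections 6.2.2, 6.3 or 9 equalises, measures or adjusts for water between these two towels.

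**2. How different could the water content be?** The towel's capacity is not given. If a full soak takes up 150 ml (assumed), a towel limited to 100 ml holds at most 100/150 = 67% of the control's water. At 200 ml (assumed) it holds at most 100/200 = 50%. At a capacity of about 100 ml or less, the two could match.

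**3. The plan's own power figure.** Section 9 states 95% power for about 0.6 log10, one-sided alpha 0.1. Section 6.3 gives 16 volunteers per round. No SD is given, so the 95% cannot be reproduced, but it can be solved for the SD of paired differences that it implies:

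- Normal formula: SD = 0.6 × √16 / (1.282 + 1.645) = 2.4 / 2.927 = 0.82.
- Paired t-test (noncentral t): 0.80.
- Signed-rank test by simulation: about 0.78.

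I take 0.8 as the central value, with 0.6 and 1.0 as the range.

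**4. What an assumed wetness bias would do.** This is a simulation of the one-sided signed-rank test with n = 16, normal differences, 40,000 runs, and rejection at a rank sum of 42 or less (exact size 0.0964). The bias values are assumptions; the documents supply none.

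Probability of declaring the dirty towel worse when dirt has no effect:

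| Loss due to wetting (log10) | SD 0.6 | SD 0.8 | SD 1.0 |
|---|---|---|---|
| 0 | 0.10 | 0.10 | 0.10 |
| 0.1 | 0.25 | 0.20 | 0.18 |
| 0.2 | 0.48 | 0.37 | 0.29 |
| 0.3 | 0.72 | 0.55 | 0.44 |
| 0.6 | 0.99 | 0.94 | 0.84 |

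Probability of detecting a true 0.6 log10 loss from dirt:

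| Wetting difference | SD 0.6 | SD 0.8 | SD 1.0 |
|---|---|---|---|
| None | 0.99 | 0.94 | 0.83 |
| Favours dirty towel by 0.3 | 0.72 | 0.55 | 0.44 |

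A bias of half the difference that the trial is sized to detect would thus be enough to mislead in either direction. The tables do not show that such a bias exists.

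**The case against.** The case on the other side has real weight.

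- **The recipe is only an example.** The pilot clause follows a list of soil, oil and water, and naturally covers all three. A reader might infer that the dirty towel is fixed at 100 ml; the text does not say so. The only stated target, however, is a towel that is visibly dirty and oily. Nothing asks that its water match the control's.
- **The mix may saturate the towel.** A towel able to take up 150 or 200 ml could hardly be immersed in about 105 ml of liquid (100 ml water plus 5 ml oil). If immersion works as described, near-saturation is at least as plausible as a dry towel. This stands, and the 67% and 50% figures should be read as no more than illustrations. With no weight recorded, though, saturation could not be shown.
- **The trial will hold some information on wetness.** The same 16 volunteers use a damp, weighed towel (Procedure 2) and a soaked, weighed clean towel (Procedure 4 control), both for 60 seconds. That contrast is not planned in section 9, but it could help. It would help with Procedure 4 only if the dirty towel's water were known.
- **Some change in wetness may belong to the condition.** If oil and soil reduce water uptake, that is part of being soiled and oily, and forcing equal water would remove it. This stands, and it argues for equal preparation rather than equal final water content.
- **The dirty towel's own log10 reduction** will be reported whatever the control does. That is also true; the concern is limited to the comparison with the clean towel.

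**Conclusion.** The point holds as a possible confounder in one of the four round 1 comparisons. Wetting differs by design between the two Procedure 4 towels, the plan itself regards wetness as a possible determinant of efficacy, and water content is neither equalised nor, as far as the text states, recorded for the dirty towel.

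A reader might go further and conclude that the dirty towel will be drier, or that Procedure 4 is certainly biased. The documents support neither: they give no capacity, no wetness effect and no direction, and the towels could match if the mix saturates the fabric. Nor does Procedure 2 show that wetness matters; it asks whether it does. The absence of a stated weighing also does not prove that none would be done.

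The error rates above rest on assumed biases and on an assumed SD of 0.6 to 1.0, of which about 0.8 is what the stated power implies. This is a cheap improvement to make before the study starts, not a defect that invalidates the trial.

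**What to change.** In section 6.2.2, Procedure 4, prepare both towels by the same steps: the same volume of water, chosen in the pilot already planned so that it is enough to soak the towel fully, and the same rubbing of the towel against itself. The only difference should be the soil and oil. State that both towels are weighed before and after preparation, and that the dirty towel's weight is read with allowance for the added soil and oil.

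This removes the difference in method while leaving any loss of water uptake caused by oil or soil as part of the condition tested. Adjusting the dirty towel to the control's water weight is not a good substitute, because one weighing cannot separate water from soil and oil.

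The cost is protocol wording, one extra weighing per volunteer, and a control preparation that departs slightly from the bucket soak used in Procedure 1. Choosing a volume that soaks the towel fully keeps that departure small and preserves the damp-versus-soaked contrast with Procedure 2.

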1.2 THE SUPERTOWEL

The Supertowel has been designed as a soap alternative for these types of emergency situations. The Supertowel is a durable fabric with a permanent anti-microbial bonding. The treated fabric must be dipped in water and then rubbed against the hands so that pathogens will be transferred to the fabric where they will be killed. Several laboratory test have demonstrated the bactericidal effect of the fabric against different bacteria (Appendix 1). The anti-microbial technology is achieved by long chains of carbon atoms attached to positively charged nitrogen atoms bonded to a silica layer of the fabric. The positively charged layer attracts negatively charged microbes including bacteria and fungi causing membrane disruption of the microbes. The Supertowel will kill microbes efficiently and within seconds once the microbe is on the towel. As the bonding is permanent the fabric does not call for replacement until it is damaged or lost. The Supertowel provides an alternative to large-scale soap distribution. It could be beneficial to emergency responders as it will be easier (smaller and lighter) to distribute and last longer than soap, negating the need for frequent distributions. The Supertowel will reduce water wastage associated with hand washing and reduce drainage problems that are often seen around hand washing facilities. The Supertowel will also be beneficial to those effected by emergencies as it can easily be carried by users all the time, making hand cleaning more convenient.

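### Section 6.2.3 does not say whether the post-value broth contains a neutralizer, and no carry-over check is described; any residual towel activity would favour the towel over soap in Procedures 1–3

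*Combined protocol and SAP*

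**What the plan says.** Section 6.2.1 recovers the pre value "in 10 ml of tryptone soya broth (TSB) without neutralizers". Section 6.2.3 recovers the post value in "separate petri dishes containing 10 ml of TSB for 60 seconds" and says nothing about neutralizers either way. Both are counted by the same plating method. No time from sampling to plating is given.

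Section 6.1 describes the test product thus: "The Supertowel is a durable fabric with a permanent anti-microbial treatment". Section 1.2 gives the chemistry as "long chains of carbon atoms attached to positively charged nitrogen atoms bonded to a silica layer of the fabric". On the comparator, Section 6.1 says: "Non-antimicrobial bar soap will be used as a reference product for three of the experiments". Those three are Procedures 1–3. Procedure 4 differs: "Control: Hand cleaning for 60 seconds with a clean Supertowel". Procedure 5 and its reference are to be designed after round 1.

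The only statement bearing on carry-over is in Section 1.2: "As the bonding is permanent the fabric does not call for replacement until it is damaged or lost".

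Under Section 9 the towel counts as equal to the reference unless its mean log10 reduction is significantly smaller. The test is a paired Wilcoxon, one-sided at 0.1, with a design difference of about 0.6 log and 95% power.

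**The concern.** A hand-wash assay of this kind should count organisms that were on the hand when it was sampled. If an active agent enters the sampling fluid with them and nothing stops it, organisms that survived on the hand may die in the dish and be counted as removed.

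In Procedures 1–3 only the towel arm could bring such an agent into the dish. The effect would therefore not cancel in the within-volunteer difference against soap; it would raise the towel's reduction and leave the soap value alone. The decision rule has no margin and passes the towel unless it is significantly worse, so an upward shift moves the result towards a pass. The fourth objective in Section 2 asks whether the towel does better than soap with contaminated water, so in Procedure 3 the same shift could also look like superiority.

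The pre value is less of an issue, because it is taken before the treatment in that run. Omitting a neutralizer there is understandable. The post value is where the question arises, and there the text is silent.

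**Working it through.** **Inputs from the documents.** 16 volunteers per round (Section 6.3), so 16 pairs per comparison; one-sided alpha 0.1, design difference 0.6 log10, power 95% (Section 9). Neither the SD of the paired differences nor any carry-over figure is given.

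**Step 1: the plan's own figure.** Without an SD the 95% cannot be reproduced, only inverted. With power = Φ(δ√n/SD − z₀.₉₀):

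SD = 0.6 × √16 / (1.2816 + 1.6449) = 2.4 / 2.9265 = 0.82.

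The paired t test and the usual efficiency adjustment for the Wilcoxon test both give 0.80. I use 0.8 as a working value and 0.6 to 1.0 as a range; these are assumptions.

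**Step 2: the bias.** Let N be the organisms surviving on the towel-wiped hand and f the share of them killed in the broth before plating. The plate then reflects N(1−f), so

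observed reduction = log10(pre) − log10[N(1−f)] = true reduction − log10(1−f).

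The shift is −log10(1−f), which is zero or positive. The soap arm has no such term. With f assumed:

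- f = 0: 0
- f = 20%: −log10(0.80) = 0.097, about 0.10 log
- f = 50%: −log10(0.50) = 0.301, about 0.30 log
- f = 75%: −log10(0.25) = 0.602, about 0.60 log

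**Step 3: effect on the test.** Suppose the towel is truly 0.6 log worse than soap. The apparent deficit is 0.6 minus the shift. At f = 50% and SD 0.8 the normal approximation gives Φ[(0.6 − 0.301) × 4 / 0.8 − 1.2816] = Φ(0.21) = 58%. Simulated signed-rank tests (20,000 runs per cell, normal differences, 16 pairs) give this power to detect the deficit:

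| Assumed f | SD 0.6 | SD 0.8 | SD 1.0 |
|---|---|---|---|
| 0 | 99% | 94% | 83% |
| 20% | 97% | 86% | 73% |
| 50% | 72% | 55% | 43% |
| 75% | 9% | 10% | 10% |

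At 75% the power has fallen to about the significance level: a deficit as large as the design difference would be invisible.

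**Step 4: where it applies.** Procedures 1–3 set an antimicrobial towel against non-antimicrobial soap, so the shift stays in the difference. In Procedure 4 both arms are towels, so this asymmetry is absent. Procedure 5 would be affected only if its reference is soap.

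**The case against.** The best defence is that the documents place the killing on the fabric. The agent is described as permanently bonded, the rapid kill in Section 1.2 refers to microbes already on the towel, and the towel itself never enters the dish. Nothing in the text describes leaching, shedding or residue on hands. This stands: it makes a small or zero f plausible, and no figure for f can be drawn from the plan. It does not settle the matter, because permanence is stated as a product property and the supplied text shows no check of it in the sampling fluid.

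A second defence is that the appendix of earlier fabric tests, the safety data sheet, the laboratory procedures and the European standard that the method adapts were not available for this review, and any of them might cover neutralization. That also stands, so the absence is claimed only for the supplied text. If such data exist, citing them would answer the point.

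A reader might infer three stronger things, none of which the documents support:

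- That post samples are known to be taken without a neutralizer. The explicit exclusion is attached to the pre value only. Plain TSB is the literal reading of Section 6.2.3, but the contrast in wording could also mean that a different fluid was intended.
- That the towel's results are inflated by 0.10 to 0.60 log. Those figures follow from assumed values of f, and the 75% case was chosen to show what would equal the design difference.
- That every towel comparison is biased in this way. Procedure 4 is not, as shown above.

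**Conclusion.** The point holds as a conditional one. The post-value fluid is under-specified on the one property that matters when an antimicrobial product is compared with a non-antimicrobial one, and the supplied text describes no carry-over control. If plain TSB is used and active residue remains on wiped hands, the bias runs in one direction, towards the towel, in Procedures 1–3 and any soap-referenced Procedure 5. This takes the soap as having no effect of its own on recovery, in line with its description as non-antimicrobial.

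The size is unknown: zero if the bonding is permanent and nothing sheds; 0.10, 0.30 or 0.60 log if 20%, 50% or 75% of survivors were killed in the broth. The power figures rest in addition on an assumed SD of the paired differences. No bias has been demonstrated. The change is worth making because it is cheap and because, without it, a favourable towel result against soap could not be separated from an assay artefact.

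**What to change.** In Section 6.2.3, state the post-value fluid in full: TSB with a suitable neutralizer, the same in all arms, soap included, so that the fluid itself cannot create a difference between arms. Before round 1, run one bench check that the fluid stops any activity derived from the towel and does not itself lower *E. coli* counts. Alternatively, cite existing data showing that nothing active carries over from the towel to the sampling fluid.

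The cost is a reagent change and one small bench validation. No volunteer procedure is added, and the design, sample size and analysis stay as they are.
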